### **8.2.5 EQ-5D**

EQ-5D (EuroQol Group, 2000) is assessed at the following time points: Month 2, Month 6, Month 12, Month 18, and Month 24. EQ-5D is also assessed at EDVs for subjects who discontinue prior to the YEV at the end of the second year.

Qualitative EQ-5D items will be summarized for Baseline and Last Value for the Efficacy Analysis Set. Additionally these parameters will be summarized for Baseline and by visit for each study visit cohort. Percentages will be relative to the number of subjects with a response to each item at each time point.

Observed values for the visual analog scale (VAS) score for general health state will be summarized for Baseline and Last Value for the Efficacy Analysis Set. Additionally observed values will be summarized for Baseline and by visit for each study visit cohort. Change from Baseline will be summarized at each visit during the Evaluation Period.

For summaries of observed values for VAS at each time point, only subjects with a change from Baseline value at that time point will be summarized.

### **8.2.6 Direct cost parameters**

Direct costs will be assessed based on concurrent medical procedures, healthcare provider consultations not foreseen by protocol, hospital stays, and ER visits.

Direct cost parameters will not be summarized but will be provided in subject data listings.

### **8.2.7 Indirect cost parameters**

The number of school or working days lost will not be summarized but will be provided in subject data listings.

### **8.2.8 Socio-professional data**

Socio-professional data are collected at the following time points: Month 12 and Month 24. Socio-professional data are also collected at EDVs for subjects who discontinue prior to the YEV at the end of the second year. These additional assessments will not be summarized but will be provided in subject data listings.

## **9 PHARMACOKINETICS AND PHARMACODYNAMICS**

Plasma samples to analyze BRV and concomitant AED plasma concentrations will no longer be obtained, as directed by the integrated protocol amendment 2.

No summaries of BRV or concomitant AED plasma levels will be provided; plasma levels will only be provided in subject data listings.

## **10 IMMUNOLOGICAL PROCEDURES**

This section is not applicable for this study.

## **11 SAFETY ANALYSES**

Safety is assessed with AEs, laboratory tests (blood chemistry, hematology, urinalysis, and pregnancy test), vital signs, body weight, ECGs, physical examination, neurological

examination, mental status, and psychiatric status. Summary tables will be provided for AEs; blood chemistry, hematology, and urinalysis; vital signs; body weight; and ECGs. No summary tables will be provided for pregnancy testing, physical examination, neurological examination, or psychiatric and mental status.

All safety summaries will be based on the Safety Analysis Set.

## 11.1 Extent of Exposure

### 11.1.1 Number of subjects exposed and subject-years of exposure

A daily dose will be calculated for each study day from the day of first dose of BRV to the day of last dose of BRV for the purposes of calculating modal dose. Daily dose will be calculated as the sum of the AM and PM dose for each day.

Modal daily doses will be calculated across all study days on or after the day of first dose of BRV and up to and including the day of last dose of BRV. Modal daily dose is the most frequently taken daily dose during this period. In the event of a tie, the modal dose will be set to the lower of the tied doses. Modal daily dose will be categorized as follows:

| Category  | Definition               |
|-----------|--------------------------|
| 5 mg/day  | <20mg/day                |
| 20mg/day  | ≥20mg/day to <50mg/day   |
| 50mg/day  | ≥50mg/day to <100mg/day  |
| 100mg/day | ≥100mg/day to <150mg/day |
| 150mg/day | ≥150mg/day to <200mg/day |
| 200mg/day | ≥200mg/day               |

Subject years of exposure will be calculated by summing the exposure duration in days for all subjects being summarized, and dividing the resulting value by 365.25.

Subject years of exposure will be presented overall and by modal dose for the Safety Analysis Set. The subject years of exposure presented by modal dose will be the total subject years of exposure of subjects with that modal dose.

The number and percentage of subjects exposed to BRV will be summarized overall and by modal dose category. The number and percentage of subjects in each Exposure Duration Cohort (≥3 months, ≥6 months, ≥12 months, and so forth) will be summarized.

The number and percentage of subjects within each modal dose category will be summarized for each Exposure Duration Cohorts; percentages will be relative to the total number of subjects in each Exposure Duration Cohort.

In addition to the overall summaries of the above, the above will also be summarized by subgroup for region.

## 11.2 Adverse Events

### 11.2.1 Definition of treatment-emergent AE

AEs will be classified as either pre-study or treatment-emergent. Pre-study AEs are defined as AEs which had onset prior to the date of the first dose of BRV for N01315. TEAEs are defined as AEs that had onset on or after the day of first BRV dose. AEs with an incomplete

onset date will be classified as TEAEs if the month and year of onset (when only the month and year are specified) is the same as the month and year of the first BRV dose or the year of onset (when only year is specified) is the same as the year of first BRV dose.

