11.1.16 Adverse Events (AEs)

At the EV, the Investigator will record any AE that was still ongoing at the end of the previous study in the source documentation. From the EV onwards, adverse events will be assessed at each visit and recorded in the CRF and in the source documents. The study participant will be given the opportunity to report AEs spontaneously. A general prompt will also be given to detect AEs, e.g., “Did you notice anything unusual about your health (since your last visit)?” In addition, the Investigator should review any self-assessment procedures (e.g. DRCs) used in the study.

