12. ADVERSE EVENTS AND SERIOUS ADVERSE EVENTS

12.1 Adverse Events

12.1.1 Definition of Adverse Event (AE)

An adverse event is any untoward medical occurrence in a subject or clinical investigation subject administered a pharmaceutical product which does not necessarily have a causal relationship with this treatment. An adverse event can therefore be any unfavorable and unintended sign (including an abnormal laboratory finding), symptom, or disease temporally associated with the use of a medicinal (investigational) product, whether or not related to the medicinal (investigational) product.

In order to ensure complete safety data collection, all AEs or undesirable experiences occurring during the study (i.e., after signature of the Informed Consent), including any pre- and post-treatment periods required by the protocol, must be reported in the CRF even if no investigational product was taken but specific study procedures were conducted. These include all AEs not present prior to the initial visit and all AEs which recurred or worsened after the initial visit.

Signs or symptoms of the condition/disease for which the investigational product is being studied should be recorded as AEs only if their nature changes considerably or their frequency or intensity increases in a clinically significant manner as compared to the clinical profile known to the Investigator from the subject's history or the Baseline Period.

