13.1.2 Safety, Efficacy, and Other Variables

13.1.2.1 Primary Safety Variables

- Occurrence of a TEAE
- Withdrawal due to AE
- Occurrence of an SAE

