### **3.2.3 Summaries at Study Entry**

The study Entry Visit (EV) corresponds to assessments performed at the time of entry into N01315. There are 2 groups of subjects to consider:

1. Subjects who immediately entered N01315 after completing the Evaluation Period or meeting the protocol defined exit criteria for N01276 and N01306
2. Subjects who did not immediately enter N01315 and had a gap in treatment with study drug between the previous study and N01315

Subjects in category 1 will generally not have any interruption in study drug dosing during the transition to N01315. Subjects in category 2 had minimal gaps in treatment, which will not change how the data are analyzed. For subjects in both categories, selected assessments from Visit 8 of the previous study will be summarized at EV. Subjects who met exit criteria in the prior study will have data from EDV used as EV for N01315.

For the assessments that were performed for all subjects at Visit 8/EDV of the previous study, the following assessments will be summarized at EV: vital signs, weight, physical examination, neurological examination, ECGs, recording of seizures, and laboratory parameters.

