### 11.2.2 General summaries of TEAEs

Pre-treatment AEs will be provided in a subject data listing; no summaries of pre treatment AEs are planned.

An overall summary of AEs will provide the overall number of TEAEs and the numbers and percentages of subjects with at least 1 TEAE, with a TEAE that led to permanent discontinuation of study drug, with a drug-related TEAE, with a severe TEAE, with a treatment-emergent SAE, and with a drug-related treatment-emergent SAE. The number and percentage of subjects who died will also be summarized. This summary will be provided for all subjects in the Safety Analysis Set and also by subgroup for geographic region.

The following summaries of TEAEs will be provided by MedDRA SOC and PT. All summaries are for the combined Evaluation, Down-Titration, and Post-Treatment Periods unless otherwise indicated.

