### *Discontinuations due to TEAE*

- Incidence of TEAEs leading to permanent discontinuation of study drug

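### Two primary safety variables carry no onset limit, but the SAP's AE tables count only events starting on or after the first N01315 dose, so a carried-over AE that ends treatment or becomes serious at unchanged intensity is left out

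*SAP*

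**What the plan says.** Protocol 13.1.2.1 lists three primary safety variables. The first is restricted to treatment-emergent events. The second, "Withdrawal due to AE", and the third, occurrence of an SAE, are not. SAP 2.2.1.1 repeats the list with the same distinction.

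SAP 11.2.1 sorts AEs by onset alone. On one side, "Pre-study AEs are defined as AEs which had onset prior to the date of the first dose of BRV for N01315"; on the other, "TEAEs are defined as AEs that had onset on or after the day of first BRV dose". SAP 3.2.1 confirms that the first dose means the first dose in N01315. SAP 11.2.1 has no clause for an earlier AE that later worsens, becomes serious or ends treatment.

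SAP 11.2.2 then restricts both unrestricted variables. The discontinuation table is "Incidence of TEAEs leading to permanent discontinuation of study drug", the SAE table covers treatment-emergent SAEs, and the overview rows are restricted in the same way. Earlier AEs are called pre-treatment and go to a listing: "no summaries of pre treatment AEs are planned". SAP 2.5, which records departures from the protocol analysis, mentions only the monotherapy endpoint.

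**The concern.** The first N01315 dose is not the start of BRV exposure. SAP 2.3 says that subjects came from N01276 or N01306, and Protocol 6.4 describes those trials as testing BRV 50 and 100 mg/day against a historical control. On transition, SAP 3.2.3 says: "Subjects in category 1 will generally not have any interruption in study drug dosing during the transition to N01315". An AE that began in the parent trial may therefore have begun on BRV, although the SAP labels it pre-treatment.

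The primary objective is long-term safety and tolerability. A subject who has lived with the same level of fatigue since the parent trial and finally stops BRV because of it is a long-term tolerability failure. Under the stated rule that event is absent from the tables that report AE discontinuation by term. The disposition table and the AE discontinuation row could then disagree, with nothing in the plan to explain why.

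**Working it through.** There is no stated figure to reproduce: the study is descriptive and SAP 2.4 gives no sample size calculation. The check is to follow an AE with onset before the first N01315 dose through the rules.

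1. **It persists unchanged, with no consequence.** It is listed only. This does not affect the two variables.
2. **Its intensity rises during N01315.** Protocol 12.1.5 requires a repeated AE record with its own start date. That date falls on or after the first dose, so the record is a TEAE and is counted.
3. **It resolves and recurs.** Protocol 12.1.1 makes recurrence after the initial visit reportable. The recurrence has its own onset, so it is counted.
4. **It stays at the same intensity and BRV is stopped because of it.** No repeated record is triggered and the original onset stands. The subject is missing from the AE overview row and from the SOC/PT discontinuation table. SAP 5.1 can still count the subject under the disposition reason ADVERSE EVENT, which has no onset limit but also no AE term.
5. **It stays at the same intensity and meets a seriousness criterion.** Intensity (Protocol 12.1.3) and seriousness (Protocol 12.2.1) are separate attributes, so this is possible. The event is missing from the treatment-emergent SAE table. Disposition helps only if the subject also withdraws for it.
6. **It is fatal.** SAP 11.2.2 counts deaths without a treatment-emergent qualifier, so the death is counted.
7. **Its onset date is partial.** If the month and year, or the year alone when only that is known, match the first N01315 dose, SAP 11.2.1 classes it as a TEAE. A parent-trial AE can then be counted.

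The omission is confined to paths 4 and 5.

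Data capture is a further weak point. Protocol 11.1.16 says: "At the EV, the Investigator will record any AE that was still ongoing at the end of the previous study in the source documentation". Protocol 12.1.1 describes what must be reported: "These include all AEs not present prior to the initial visit and all AEs which recurred or worsened after the initial visit". Neither sentence clearly requires an unchanged, ongoing parent-study AE to have an N01315 CRF entry when it ends treatment.

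**Scale.** The only input is 108 enrolled (SAP 2.4), assumed here to equal the Safety Analysis Set. Understatement in percentage points = 100 × k / 108, where k is the number of subjects omitted. The documents give no k, so these values are assumptions:

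- k = 0: 0
- k = 1: 100 × 1/108 = 0.93
- k = 2: 100 × 2/108 = 1.85
- k = 3: 100 × 3/108 = 2.78
- k = 5: 100 × 5/108 = 4.63

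**The case against.** The strongest reply is that little is lost. AE withdrawals are counted in disposition whatever the onset. The intensity grades in Protocol 12.1.3 include functional and clinical consequence, so an AE that comes to need hospitalization would usually move up a grade and be re-reported. The SAE gap is then mainly AEs that were already severe. Every SAE must also reach the sponsor within 24 hours (Protocol 12.2.2). All of this stands, and it keeps the point small. It does not supply the missing AE term or a row in the primary-variable tables, and SAEs have no general fallback equivalent to disposition.

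It can also be argued that Protocol 13.1.3.1 introduces the withdrawal and SAE tables directly after a sentence on TEAEs, so they may be meant as TEAE subsets. That reading is plausible. A conflict with that section is arguable, but the variable lists in both documents remain unrestricted.

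A reader might infer more than the documents support:

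- **Carried-over AE withdrawals vanish altogether.** They do not; disposition retains them by reason.
- **Every subject enters while taking BRV.** SAP 3.2.3 describes a second group with a treatment gap, which it calls minimal. Prior exposure is universal; uninterrupted dosing is not.
- **The AE tables can only understate.** The partial-date rule can push counts up.
- **Carried-over AEs never reach the database.** Protocol 11.1.16 goes on to require CRF recording of AEs from the Entry Visit onwards, and the planned listing of pre-treatment AEs presupposes that some are held.

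**Conclusion.** The point holds in a narrow form. The SAP applies an onset-only filter, anchored to the first N01315 dose, to two of three primary safety variables that are defined without one, and SAP 2.5 does not declare it. Followed as written, it omits from the AE overview and SOC/PT tables any AE with earlier onset that ends treatment, or less often becomes serious, without a rise in intensity. For those events the omission understates the tables.

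The number affected is unknown and may be zero. Each subject is about 0.93 percentage points if the Safety Analysis Set is all 108 enrolled, and slightly more if it is smaller. The conclusion assumes that investigators follow the repetition rule and that the AE tables are programmed as SAP 11.2.1 and 11.2.2 read. No hypothesis test or decision rule is affected. It is still worth correcting, because the omitted events bear directly on the primary objective.

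**What to change.** In SAP 11.2.2, tabulate all AEs leading to permanent discontinuation of study drug on or after the first N01315 dose, and all AEs that are or become serious on or after that dose, whatever the AE onset date. Keep the TEAE row and show AEs with earlier onset in a separate row beside it, by SOC and PT. Reconcile the discontinuation count with the disposition reason ADVERSE EVENT and footnote any difference. Record the change in SAP 2.5.

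Identify carried-over cases from the N01315 AE and termination CRFs and the listing of pre-treatment AEs, with a query to source where the term is missing. The parent-study database should not be assumed to supply the term: AEs are not among the items that Protocol 5.1 and 11.2.1 take from it at entry, and a parent record need not show which event later ended treatment.

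The cost is SAP wording, one extra row in two tables and a few queries. The reported figures may become slightly less favourable.

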### 11.2.2 General summaries of TEAEs

Pre-treatment AEs will be provided in a subject data listing; no summaries of pre treatment AEs are planned.

An overall summary of AEs will provide the overall number of TEAEs and the numbers and percentages of subjects with at least 1 TEAE, with a TEAE that led to permanent discontinuation of study drug, with a drug-related TEAE, with a severe TEAE, with a treatment-emergent SAE, and with a drug-related treatment-emergent SAE. The number and percentage of subjects who died will also be summarized. This summary will be provided for all subjects in the Safety Analysis Set and also by subgroup for geographic region.

The following summaries of TEAEs will be provided by MedDRA SOC and PT. All summaries are for the combined Evaluation, Down-Titration, and Post-Treatment Periods unless otherwise indicated.

#### *Overall Incidence Summaries*

- Incidence of TEAEs
- Incidence of TEAEs by 3-month time interval
- Incidence of TEAEs by study period (Evaluation, Down-Titration, Post-Treatment)
- Incidence of TEAEs for TEAEs occurring in at least 5% of subjects
- Incidence of TEAEs by 3-month time intervals for TEAEs occurring in at least 5% of subjects overall
- Incidence of non-serious TEAEs occurring in at least 5% of subjects

The incidence of TEAEs occurring in at least 5% of subjects will be summarized overall as noted above and also by subgroup for geographic region.

A subject is included in a 3-month interval if the subject was receiving BRV at any time during that interval based on their duration of exposure to BRV (eg, a subject with exposure for 91 days is included in the time interval for Months 1-3 and Months 4-6). Summaries of AEs by 3-month intervals will include all subjects who are classified into each time interval as defined above. TEAEs which had onset prior to or on the date of the last dose of BRV (or the date of last scheduled or unscheduled visit for subjects who are ongoing at the time of the clinical cutoff) are included in summaries by 3-month time intervals.

#### *Maximum Intensity and Causality*

- Incidence of TEAEs by maximum intensity
- Incidence of drug-related TEAEs

#### *Serious Adverse Events*

- Incidence of treatment-emergent SAEs

### *Discontinuations due to TEAE*

- Incidence of TEAEs leading to permanent discontinuation of study drug

### *TEAEs of interest*

AEs of interest will be identified based on MedDRA search criteria, which are documented outside of the SAP. The following summaries will be provided for AEs of interest:

- Incidence of TEAEs of interest
- Incidence of TEAEs of interest by 3-month time interval

For the summary by maximum intensity, each subject will be counted at most once per SOC or PT according to the maximum intensity of all AEs within that SOC or PT. Severe intensity will be assumed for AEs for which intensity is not specified.

Drug-related AEs are AEs for which the relationship to study drug is specified as Related or AEs for which relationship is not specified.

## **11.3 Clinical Laboratory Evaluations**

Clinical laboratory parameters (blood chemistry, hematology, urinalysis) are assessed at all FEVs, YEVs, EDVs, and at FV, and may also be assessed at Unscheduled Visits.

### **11.3.1 Hematology and blood chemistry parameters**

Observed values for each planned hematology and blood chemistry parameter will be summarized for Baseline, Study Entry, and each scheduled visit during the Evaluation Period for which laboratory parameters were assessed, Last Value, EDV, and FV. Change from Baseline will be summarized for all post-Baseline time points including EV. Only laboratory parameters planned per protocol will be summarized; results for laboratory parameters not planned per the protocol will only be provided in subject data listings.

The number and percentage of subjects with an on-treatment potentially clinically significant treatment-emergent (PCST) value, PCST low value, and PCST high value will be summarized. This summary will consider all assessments after the first dose of BRV and prior to or on the date of the last dose of BRV. Percentages will be relative to the number of subjects with an on-treatment assessment.

Additionally, the number and percentage of subjects with a PCST value, PCST low value, and PCST high value will be summarized for Baseline, Study Entry, each visit during the Evaluation Period for which laboratory parameters were scheduled to be assessed, EDV, Last Value, and FV. Percentages for each parameter and time point will be relative to the number of subjects with a value at that time point.

PCST (Sections 13.3.1, 13.3.2, and 13.3.3) criteria are based on FDA Division of Neuropharmacologic Drug Products guidelines with some UCB-defined additions.

Creatinine clearance, when available from the central laboratory, will be provided in subject data listings only and will not be summarized.

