9.2 Subject Exclusion Criteria

Subjects must be excluded if they meet any of the following criteria:

- Severe medical, neurological and psychiatric disorders, including current suicidal ideation or behaviour, or laboratory values which may have an impact on the safety of the subject, as determined by the Investigator.
- Poor compliance with the visit schedule or medication intake in the previous BRV study.
- Participation in any clinical study of another investigation drug or device during the study.
- Pregnant or lactating woman.

If the Investigator has any medically valid reason to doubt the eligibility of a subject, the subject should not be included into the study. If, however, the Investigator has any other kind of doubts concerning the subject's eligibility, he/she should consult the UCB Study Physician or representative for clarification.

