## **2.4 Determination of Sample Size**

No sample size calculation was done. Sample size was dependent upon recruitment into and completion of preceding studies. At the time of development of this SAP, the enrollment into this study has been completed and a total of 108 subjects have been enrolled into N01315.

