### **3.3 Definition of Baseline Values**

Baseline for all study outcomes will be based on baseline from the previous studies. For assessments performed at scheduled and unscheduled visits, Baseline will generally be the last result obtained or prior to the randomization visit of the previous study. Baseline will be defined separately for each hematology, blood chemistry, and urinalysis parameter.

Baseline for the evaluation of seizure frequency and seizure days will be calculated from the core study seizure diary based on the rules defined in Section 3.8.1.

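### SAP 11.3.1 labels laboratory values treatment-emergent, but every summarised haematology and chemistry criterion except GGT lacks a baseline condition, so abnormalities persisting from the parent-study Baseline are counted as emergent.

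*SAP*

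**What the plan says.** For each planned haematology and chemistry parameter, SAP 11.3.1 gives the number and "percentage of subjects with an on-treatment potentially clinically significant treatment-emergent (PCST) value", and does the same for low and high values separately. On the window it states: "This summary will consider all assessments after the first dose of BRV", up to and including the date of the last dose. On the denominator: "Percentages will be relative to the number of subjects with an on-treatment assessment". On scope: "Only laboratory parameters planned per protocol will be summarized"; creatinine clearance is listed only. The section also tabulates PCST counts at Baseline, Study Entry, each scheduled laboratory visit, EDV, Last Value and FV.

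The limits are in SAP 13.3.1 (haematology) and 13.3.2 (chemistry). The GGT row counts a value of at least 3 times ULN only if the baseline value was no more than 3 times ULN. No other row in these two tables mentions baseline.

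SAP 3.3 sets the anchor: "Baseline for all study outcomes will be based on baseline from the previous studies", generally the last result up to the randomisation visit there. It adds: "Baseline will be defined separately for each hematology, blood chemistry, and urinalysis parameter". It gives no rule for when a laboratory value is emergent.

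Protocol 13.1.3.1 commits to listing and summarising possibly clinically significant abnormalities that are treatment-emergent.

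**The concern.** An emergent abnormality is one that was not there before treatment. As written, the laboratory count asks only whether the limit was met at some on-treatment assessment. A subject whose value was already beyond the limit before randomisation in the parent study, and stays there, enters the numerator as an emergent case. A subject who could not have become newly abnormal also stays in the denominator.

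The study has one arm, so no control group carries the same background of persisting abnormalities. The percentage mixes old and new findings under a label that promises only new ones. Long-term safety is the primary objective, and a reader will take the label at face value.

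**Working it through.** **1. Which criteria are summarised.** SAP 13.3.1 has 10 rows and 13.3.2 has 21, so 31 in all. Creatinine clearance is listing-only. BUN, globulin, HDL, LDL and triglycerides are not named in Protocol 11.1.15, so they fall outside the planned parameters. 31 − 6 = 25. This counts total cholesterol, which Protocol 11.1.15 says was collected until approval of Amendment 2.

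**2. Which of these refer to baseline.** Only GGT. The ALP qualifier for subjects under 17 concerns an age-adjusted normal range, not the baseline value. 25 − 1 = 24 rows state a limit alone. The count depends on how cholesterol testing is read; the exception does not:

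| Rows counted | Total | No baseline condition |
|---|---|---|
| Without cholesterol | 24 | 23 |
| With total cholesterol | 25 | 24 |
| Also HDL and LDL | 27 | 26 |
| Also triglycerides | 28 | 27 |
| All rows in both tables | 31 | 30 |

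**3. Whether another section supplies the rule.** SAP 3.3 defines Baseline but not emergence. Elsewhere in the appendix the condition is written out: urinalysis needs an upward shift of at least 2 degrees from baseline (13.3.3), and pulse, blood pressure and adult weight need a stated change from baseline (13.3.4). SAP 11.3.1 itself tabulates PCST values at Baseline. A value at a pre-treatment Baseline cannot be emergent, so for the limit-only rows PCST works as a threshold. A programmer following the text would add no baseline condition.

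**4. What the Baseline column can show.** It gives marginal counts only. Suppose 3 subjects met a limit at Baseline and 5 met it on treatment (assumed). The overlap can be anything from 0 to 3, so the number newly abnormal can be anything from 5 − 3 = 2 to 5 − 0 = 5.

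**5. Size, as illustration.** The documents give no figure to reproduce. Take one parameter and N = 108, since SAP 2.4 says "a total of 108 subjects have been enrolled into N01315". Assume that all 108 have a Baseline and an on-treatment value, that m = 2 are newly abnormal, and that k met the limit at Baseline and all still meet it on treatment.

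- SAP percentage = (m + k)/N
- Rate among those not meeting the limit at Baseline = m/(N − k)

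| k (assumed) | SAP percentage | Rate among those not abnormal at Baseline |
|---|---|---|
| 0 | 2/108 = 1.9% | 2/108 = 1.9% |
| 1 | 3/108 = 2.8% | 2/107 = 1.9% |
| 3 | 5/108 = 4.6% | 2/105 = 1.9% |
| 5 | 7/108 = 6.5% | 2/103 = 1.9% |

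When new events are few, a handful of persisting ones dominates the reported figure.

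**The case against.** The best defence is that this is mainly a matter of naming. The SAP uses PCST as the name of a limit, tabulates it at Baseline and Study Entry, and also reports observed values, changes from Baseline and listings. A careful reader can see that some abnormalities predate treatment. That is right as far as it goes, and it is why renaming is the first step of the fix. It does not supply the within-subject link, and a listing does not correct a percentage.

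Second, persisting cases may be rare. Several limits lie far from normal (sodium at or below 115 mEq/L in adults, AST or ALT at least 3 times ULN, platelets at or below 75 x 10^9/L). Protocol 9.2 also excludes subjects with "laboratory values which may have an impact on the safety of the subject, as determined by the Investigator". This stands as a limit on the likely size. It is a judgment-based exclusion, though, and milder limits such as eosinophils at 10% or more can plausibly be met before treatment.

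Third, counting every on-treatment value beyond a limit is the inclusive choice for a safety study: it over-counts rather than hides. This also stands. Simply removing subjects who were abnormal at Baseline would lose sight of any who then worsened. The present counts should therefore stay, under an accurate name.

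Fourth, the SAP says the criteria follow FDA division guidelines with sponsor additions. That source is not in the documents, so nothing can be said about whether limit-only rows depart from it.

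**Conclusion.** The point holds on the text. For every summarised haematology and chemistry criterion except GGT, SAP 11.3.1 counts a limit already met at the parent-study Baseline and still met on treatment as treatment-emergent, and no planned table separates these cases from new ones. That does not deliver what Protocol 13.1.3.1 promises. It should be corrected before the final analysis, but its reach is limited: laboratory tests are other safety variables and all summaries are descriptive.

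A reader might infer three stronger things that the documents do not support:

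- **That the laboratory results are inflated.** The number of affected subjects is not given and may be zero. The percentages above rest wholly on assumed values of m and k and on complete data for 108 subjects.
- **That 24 of 25 is a firm count.** It needs total cholesterol to be planned and HDL, LDL and triglycerides not to be. The firm statement is that GGT is the only exception under any count.
- **That the PCST scheme ignores baseline altogether.** It does not: urinalysis, pulse, blood pressure and adult weight are judged against it.

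**What to change.** Amend SAP 11.3.1 as follows.

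1. Rename the existing on-treatment and by-visit counts as values meeting the potentially clinically significant limit. Keep their present denominators. GGT keeps its own baseline clause.
2. Add one on-treatment row per parameter and direction for treatment-emergent values: limit met on treatment and not met in that direction at the parent-study Baseline. The denominator is subjects with an on-treatment value and a Baseline value not meeting that limit. Show subjects with a missing Baseline separately.
3. Add a within-subject shift table from Baseline to on-treatment, using the lowest on-treatment value for the low direction and the highest for the high direction. The categories are limit not met, limit met, and missing. For subjects who met the limit at Baseline, list the Baseline value and the most extreme on-treatment value, so that further worsening stays visible.
4. Footnote that the anchor is the pre-randomisation Baseline of the parent study (SAP 3.3). Values that first cross a limit during the parent study and still meet it on treatment here therefore count as emergent, and those present at entry appear in the Study Entry column. This differs from the adverse-event rule in SAP 11.2.1, which starts at the first dose in N01315.

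The cost is SAP wording, a derived flag, one extra row per parameter and direction, one extra table and a short listing. No new data are needed, because Baseline is already defined per parameter.
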